8.3 Statistical methods

Part 1: The primary hypothesis is that there is no difference in the results of PFT and rPFT for respiratory assessment of FVC and MIP. We will use a paired sample t-test to determine if the mean test results are comparable between the standard and experimental treatments. We will conduct a qualitative analysis to determine whether the patient, caregiver, and therapist determine the rPFT to be an effective way to conduct tests of breathing function.

Part 2: Aim 1 will be analyzed to determine if the study date of NIV initiation is at least 30 days sooner based on rPFTs compared to standard clinic PFTs. This will be done using a non-parametric two sample test of means, the Wilcoxon-Mann-Whitney rank sum test. For analysis of Aim 2, a linear mixed effects model will be used to analyze the change from baseline between study groups of self-efficacy scores and respiratory health [Verbeke2000]. The effect size will be quantified from the model using the difference in means between the groups with their associated 95% confidence intervals.

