1.0 Objectives

1.1 Study Objectives

The specific objective of this proposal is to utilize the practice of telemedicine via connected health devices to enable the guided performance of a remote pulmonary function test (rPFT) in the home. The rationale for this study is to determine whether telemonitoring of respiratory health can help exceed standards of ALS care.

Part 1: Demonstrate the reliability of remote pulmonary function testing, performed via telemedicine, for monitoring respiratory function in patients with amyotrophic lateral sclerosis (ALS)

Primary Hypothesis: There is no difference in the results of PFT and rPFT for respiratory assessment of FVC and MIP.

Secondary Hypothesis: The respiratory therapist, patient, and caregiver will express confidence in conducting the rPFT, as determined by surveys of procedure acceptance.

Part 2: Weekly remote pulmonary function testing (rPFT) and nurse respiratory health coaching (NRHC) in ALS telemedicine

This part randomizes subjects into two arms – both perform weekly rPFT testing and one receives monthly NRHC.

Aim 1: Clinically-meaningful benefit of weekly rPFT

Primary Hypothesis: Home respiratory assessment enables thresholds for non-invasive ventilation (NIV) recommendation to be met on average 30 days sooner when measured weekly compared to the standard 3-month interval.

Secondary Hypothesis: Determine the factors associated with adherence to weekly rPFT procedures.

Aim 2: The impact of NRHC on patient outcomes

Primary Hypothesis: Patient and caregiver teams in the NRHC arm report higher self-efficacy in the respiratory management of the disease at 6 months compared to those in the non-NRHC arm.

Secondary Hypotheses: Patients in the NRHC arm report higher self-efficacy at 12 months, experience less decline of respiratory-related quality of life and fewer respiratory complications compared to those in the non-NRHC arm.

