2.2 Previous Data

Preliminary work by our group as part of a pilot study assessing the benefits of ALS telemedicine has shown that the practice of live telemedicine is viewed favorably by ALS patients, caregivers, and multidisciplinary ALS team members, although less so by the latter group (Figure 1, [Morris2016, Geronimo2017]). Overall, the three rater groups were concerned that the lack of physical contact lessened the ability for providers to deliver equal care. This led us to identify and act upon one area of care that could be improved in telemedicine – assessment of breathing function.

[figure not shown]

Figure 1: Patient (P), caregiver (C), and health care provider (H) ratings of the ALS telemedicine pilot in four domains [Geronimo2017]. Circles containing an X mark the medians, thick lines span the first to third quartile of data, with thin lines extending up to two times this range. Outliers are those small circles outside this range

From January to September 2018, the procedures for part 1 were completed in forty patients. The main result was that the simulated remote assessment produced similar values of FVC and MIP compared to standard assessments (Figure 2). In this sample, the specificity and sensitivity of FVC measurements were 100%, for MIP assessments was 89% and 82%, respectively [Geronimo2019]. The results of part 1 indicate that rPFTs are accurate and acceptable measures of respiratory health.

[figure not shown]

Figure 2: FVC (Left) and MIP (Right) data from 40 subjects of the rPFT pilot study, comparing standard PFT measures to therapist-guided remote assessments. Four shaded quadrants are created by segmenting standard and remote tests by predefined clinical thresholds.

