8.0 Subject Numbers and Statistical Plan

8.1 Number of Subjects

Approximately (but no more than) 123. We will enroll **40 patient/caregiver teams for Part 1** and up to **60 patient/caregiver teams for Part 2** to achieve 40 pairs completing procedures for Part 2.

Participants in the two studies may overlap. Up to **20 practice control participants** may be recruited for Part 1. Up to **three respiratory therapists** will also be recruited for these studies.

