8.2 Sample size determination

Our sample size is predetermined based on our subjective ability to recruit patients within the time frame of the study. Power analysis was based on studies of FVC decline. Lo Coco et al., [LoCoco2006], showed that 50% of study participants dropped below 50% predicted FVC in one year. Given that our exclusion criteria for Part 2 will reject many of the 37% of individuals in their study who were “slow progressors,” we estimate that 75% of patients enrolled in our study will meet the respiratory criteria to recommend NIV. This results in a sample size per arm of n=15, which provides 80% power to detect a difference in mean outcome between the two groups if the effect size is found to be 0.95.

Assuming a monthly change in FVC of $3.5 \pm 3.4\%$ found by Schiffman et al. [Schiffman1993], we conducted 10,000 Monte-Carlo simulations of 40 participants declining at this rate for 12 months. Half were sampled once every three months, and half were sampled every month. $80.6 \pm 6.3\%$ of simulated participants met the requirements for NIV recommendation, in roughly equal proportions across groups. The average FVC at recommendation was 47.0% predicted in the experimental group, and 43.4% predicted in the control group. The effect size of the difference in FVC between groups was $.964 \pm .343$.

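### Part 1's paired t-test of means cannot show that remote and standard tests agree; section 8.3 needs an agreement analysis of the 40 pairs, separately for FVC and MIP

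*Combined protocol and SAP*

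**What the plan says.** Section 1.1 gives the aim of Part 1 as "Demonstrate the reliability of remote pulmonary function testing", with the primary hypothesis "There is no difference in the results of PFT and rPFT for respiratory assessment of FVC and MIP". Section 8.3 repeats that hypothesis and names one quantitative method: "We will use a paired sample t-test to determine if the mean test results are comparable between the standard and experimental treatments". The rest of the Part 1 analysis there is a qualitative look at acceptance. Section 8.3 gives no equivalence margin, confidence interval for the paired difference or limits of agreement for Part 1.

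Section 8.1 sets the size at "40 patient/caregiver teams for Part 1". Section 8.2 bases the number on recruitment, "Our sample size is predetermined based on our subjective ability to recruit patients within the time frame of the study", and its power text concerns FVC decline in Part 2.

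Section 2.2 reports that Part 1 was completed in forty patients in 2018. It states that values were similar, gives FVC sensitivity and specificity of 100%, and gives specificity and sensitivity "for MIP assessments was 89% and 82%, respectively". It concludes: "The results of part 1 indicate that rPFTs are accurate and acceptable measures of respiratory health".

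**The concern.** A t-test is built to reject equality of means. When equality is what the study wants to show, failing to reject is weak evidence for it, and a small or noisy sample makes that outcome easier to reach. A device that scatters widely around the standard reading is more likely to pass than a precise one with the same bias.

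A mean difference also lets positive and negative errors cancel. The readings are used one patient at a time: under section 7.2.2, a single FVC or MIP value past its threshold is forwarded to the clinical team. Reliability for that use is a matter of individual agreement, which the planned test does not address.

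At stake is how far the Part 1 accuracy statement can be relied on, above all for MIP, where the reported threshold results are weaker than for FVC.

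**Working it through.** **Inputs.** From the documents: 40 pairs (8.1, 2.2); MIP specificity 89% and sensitivity 82% (2.2); mean FVC decline of 3.5 points a month, a simulation input for Part 2 (8.2). Assumed, because not stated: two-sided 5% for the t-test; one-sided 5% for each of the two one-sided equivalence tests (TOST); SD of paired FVC differences of 5 to 10 points of % predicted. The plan gives no Part 1 power figure to reproduce.

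**1. What non-significance would mean.** For a true bias of d SDs of the paired differences, the t statistic has 39 degrees of freedom and noncentrality d × √40 = 6.325 d.

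| True bias (SD) | Noncentrality | Chance of p > 0.05 | In points if SD = 5 | In points if SD = 10 |
|---|---|---|---|---|
| 0.2 | 1.26 | 77% | 1.0 | 2.0 |
| 0.3 | 1.90 | 54% | 1.5 | 3.0 |
| 0.4 | 2.53 | 31% | 2.0 | 4.0 |

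Power reaches 80% only at a bias of 0.454 SD.

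**2. What would pass.** The 95% CI half-width for the mean difference is t(0.975, 39)/√40 = 2.023/6.325 = 0.32 SD, so any smaller observed bias is non-significant. At an SD of 10 points that is 3.2 points. The 90% half-width is 1.685/6.325 = 0.27 SD.

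**3. What the test does not see.** Limits of agreement are the bias ± 1.96 SD: ±9.8 points at an SD of 5 and ±19.6 at an SD of 10. Both are compatible with a non-significant t-test. With 40 pairs, each limit has a 95% CI half-width of 2.023 × √(1/40 + 1.96²/(2 × 39)) = 0.55 SD, so the limits can be estimated usefully from the data held.

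**4. The reported MIP results.** The complements are 100 − 89 = 11% of patients not meeting the criterion on the standard test and 100 − 82 = 18% of those meeting it. The overall error rate lies between the two, or about 4 to 7 of 40. If all 40 patients contributed a MIP pair, the only split that gives both rounded figures is 18 of 22 (81.8%) and 16 of 18 (88.9%), hence 4 + 2 = 6 errors. On that assumption the 95% Wilson intervals are 61% to 93% for sensitivity and 67% to 97% for specificity. The documents do not state these counts.

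**5. What an equivalence test could do.** With 40 pairs and no true bias, TOST has 80% power when the margin is about 0.47 SD or wider. For an illustrative FVC margin of 3.5 points, that requires an SD of differences of at most 3.5/0.47, about 7.4 points. The documents offer nothing from which to take a MIP margin.

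**The case against.** The strongest reply is that the completed work did not lean on the t-test. A reader might infer that the accuracy statement in section 2.2 rests on a non-significant p-value. It does not: the section cites no p-value and offers sensitivity and specificity at the clinical thresholds, with a per-patient plot. That is patient-level evidence. It stands as a reply, but only in part, because the analysis is not in section 8.3 and section 2.2 gives no intervals. Section 2.2 also cites a full report of Part 1 that is not available here, so whether limits of agreement were published is unknown.

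Three further stronger readings also go beyond the documents:

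- **That section 8.3 declares p > 0.05 a success.** It says only that the test will judge whether means are comparable. The reading follows from the hypothesis and from the absence of any other criterion, but it is an inference.
- **That MIP misclassified 11% and 18% of all patients.** These are conditional rates in two subgroups. Nor are they purely remote-test error: section 7.2.1 places the two tests 2 to 3 hours apart, and the documents give no repeatability of the standard test for comparison.
- **That Part 1's conclusion is the formal basis for Part 2.** No section states this or sets a go/no-go rule. Part 1 tested therapist-guided measurement in clinic. Part 2 uses self-administered tests at home with its own training, an aptitude check and an FVC consistency check (1.3, 7.2.2), though that consistency check does not cover MIP.

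**Conclusion.** The concern holds for the plan as written. The single quantitative analysis in section 8.3 cannot establish the Part 1 primary hypothesis. With 40 pairs it would be non-significant 77% of the time for a bias of 0.2 SD and 54% of the time for 0.3 SD, and it is silent on individual agreement. These probabilities assume a two-sided 5% test and roughly normal differences. Their size in clinical units depends on an SD that the documents do not give: 0.3 SD is 1.5 to 3 points of % predicted FVC for assumed SDs of 5 to 10.

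The reported threshold results go some way to fill the gap for FVC, less so for MIP, and they do not support one accuracy statement for both. It is not shown that remote testing is inaccurate, or that any Part 2 result would change. The point concerns what the Part 1 data can be said to demonstrate.

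**What to change.** In section 8.3, replace the t-test criterion with an agreement analysis of the 40 pairs, done separately for FVC and MIP:

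- the mean paired difference with its confidence interval;
- Bland-Altman limits of agreement with confidence intervals;
- sensitivity and specificity at the clinical thresholds, with counts and confidence intervals.

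If an equivalence margin is used, give a clinical justification for each measure and label it post hoc, since Part 1 ended in 2018. The 3.5-point FVC figure is only an illustration: it is a simulation input, not a justified tolerance. A MIP margin would need its own argument. If no margin can be justified, report the intervals descriptively.

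In section 2.2, state the accuracy conclusion separately for FVC and MIP, with the intervals beside it.

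The cost is a short re-analysis of data already held and some rewording; no new patients are needed. The MIP statement may become less favourable.

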2.0 Background

2.1 Scientific Background and Gaps

Non-invasive ventilation (NIV) lengthens survival and improves QoL for patients with ALS.

According to the Quality Measurement Set put forth by the American Academy of Neurology (AAN), two parameters of high importance in ALS care are monitoring of respiratory function and management with NIV [Miller2013]. The practice parameter of the AAN regarding ALS care states that NIV is effective in prolonging survival and slowing the rate of respiratory decline [Miller2009]. NIV has been documented to have a positive effect on QoL in the areas of sleep quality, daytime sleepiness, physical fatigue, and depression [Butz2003]. NIV is recommended when a patient presents with either an FVC \leq 50% predicted or a MIP > -60 cm H₂O [Miller2009]. It is recommended that PFTs be done at least once every three months, and that doctors discuss options for NIV support regularly.

The multidisciplinary clinical model may not provide optimal management for patients with rapidly progressing respiratory symptoms.

Although disease course varies substantially, some patients experience rapid respiratory decline. In prospective study of 38 newly diagnosed patients, half presented with chronic hypoventilation after one year, necessitating the introduction of NIV [LoCoco2006]. The authors suggest that efforts should be made to evaluate pulmonary function in these patients at least once every month. Furthermore, it has been shown that early initiation of NIV at an FVC threshold of 65% predicted was associated with a significant increase in the median time from ALS diagnosis to death [Lechtzin2007]. The current practice of quarterly respiratory assessment may leave some individuals in danger of developing to untreated respiratory insufficiency or beginning treatment later than would be optimal or other more scientific wording.

Telemedicine has impacted other areas of neurology, but is understudied for efficacy in ALS.

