3.3 Early Withdrawal of Subjects

3.3.1 Criteria for removal from study

Participants may voluntarily withdraw from the study at any time. The research team may also terminate the study if the participant does not meet the inclusion criteria or exhibits one or more of the exclusion criteria during the course of the study. For part 2 of the study, participants may be removed if they exhibit non-compliance to study procedures. Non-compliance is defined as 30 days without submission of an rPFT report if still eligible for rPFT reporting, or 3 months without a nurse coaching session if in the nurse coaching arm.

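### The 8.2 simulation samples monthly although the trial tests weekly, and the 30-day criterion equals the lead expected from monthly testing: meeting it shows a gain over quarterly testing, not that weekly testing adds to monthly

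*Combined protocol and SAP*

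**What the plan says.** The Aim 1 hypothesis in 1.1 is that home testing allows "thresholds for non-invasive ventilation (NIV) recommendation to be met on average 30 days sooner when measured weekly compared to the standard 3-month interval". The analysis in 8.3 turns this into a minimum: "Aim 1 will be analyzed to determine if the study date of NIV initiation is at least 30 days sooner based on rPFTs", against standard clinic PFTs. The caption of Figure 4 (7.2.2) defines the outcome as the time from the first identification of NIV need to the next standard clinic visit.

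Sections 7.1 and 7.2.2 have both arms testing weekly at home, with clinic PFTs about every three months. The simulation in 8.2 uses a different schedule: "Half were sampled once every three months, and half were sampled every month". Its results are on the FVC scale: "The average FVC at recommendation was 47.0% predicted in the experimental group, and 43.4% predicted in the control group", with an effect size of 0.964 (± 0.343). The power statement in the same section uses 0.95. No result is given in days, no start FVC is given, and nothing in the plan derives the 30 days.

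**The concern.** The simulated schedule is not the trial's schedule, so the design figures in 8.2 belong to monthly testing. The 30 days in 1.1 and 8.3 also coincides with what monthly testing would give. A mean lead near 30 days would meet the Aim 1 criterion, yet monthly tests would be expected to produce the same lead.

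Monthly testing is a real alternative. Section 2.1 cites a suggestion to "evaluate pulmonary function in these patients at least once every month". Under 3.3.1, "Non-compliance is defined as 30 days without submission of an rPFT report", so a participant reporting every four weeks would stay within that limit and, with accurate tests, would still be expected to show a lead of about 30 days. Section 7.3 puts the weekly schedule at about 47 home tests of 10 to 30 minutes each. A reader of the results will want to know whether that frequency earns its burden, and the criterion does not answer this.

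**Working it through.** **Inputs from the plan.** Home interval 7 days and clinic interval about three months (7.1); simulated intervals one and three months, FVC decline 3.5 ± 3.4 points a month, 12 months, FVC at recommendation 47.0% and 43.4%, 80.6% of simulated participants reaching the criterion, effect size 0.964 (8.2); FVC threshold 50% (2.1, 7.2.2).

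**Assumptions.** Start FVC 82%, varied from 75% to 90%; accurate tests; FVC trigger only; full adherence. The decrement is redrawn each month, or alternatively held fixed for each patient.

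**1. Calendar arithmetic.** If the crossing falls uniformly within a clinic interval, the expected lead is (clinic interval − home interval)/2.
- Monthly: (91.3 − 30.4)/2 = 30.4 days.
- Weekly: (91.3 − 7)/2 = 42.2 days.
- Weekly over monthly: (30.4 − 7)/2 = 11.7 days.

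**2. The plan's own FVC gap in days.** (47.0 − 43.4)/3.5 = 1.03 months, about 31 days. This matches the monthly figure.

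**3. Reproducing 8.2, then changing only the sampling interval** (start 82%, decrement redrawn monthly):

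| Sampling | FVC at recommendation | Effect size v quarterly | Lead over quarterly |
|---|---|---|---|
| Quarterly | 43.5% (plan 43.4%) | – | – |
| Monthly | 47.0% (plan 47.0%) | 0.95 (plan 0.964) | 30 days |
| Weekly | 49.3% | about 1.7 | 41 days |

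About 81% of simulated patients cross the threshold, against the plan's 80.6%. The plan's figures are recovered with monthly sampling and not with weekly sampling.

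**4. Sensitivity.** Over start FVC 75–90%, with decrements redrawn or fixed for each patient, the lead is about 27–31 days for monthly and 37–42 days for weekly sampling. The weekly effect size is 1.6–1.8, and FVC at recommendation stays near 49%.

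**5. Test noise.** With an assumed measurement SD of 3 points and a single-crossing rule, weekly FVC at recommendation falls to about 47.9% and the effect size to about 1.3. The lead over the date at which quarterly testing itself detects the crossing rises to 31–35 days (monthly) and 54–63 days (weekly), partly through false early crossings. The gap between the schedules remains.

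**6. Paired comparison within participants.** Thinning each simulated weekly series to every fourth test delays the first crossing by about 11 days on average. Simple arithmetic agrees: (28 − 7)/2 = 10.5 days. The SD of the difference is about 8 to 11 days, so with 30 crossers (75% of 40, from 8.1 and 8.2) the 95% half-width is 1.96 × 8/√30 = 2.9 to 1.96 × 11/√30 = 3.9 days.

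**The case against.** The strongest reply is that weekly against monthly is not a question the plan asks. Section 1.1 fixes the comparator as the three-month interval, Aim 1 is titled as a clinically meaningful benefit, and 8.3 sets a minimum. A clinical floor need not equal the theoretical yield of a schedule, and it is no error that another schedule would also reach it. This stands. A reader might infer that a 30-day lead cannot show any benefit of weekly testing; the documents do not support that, because it would show the stated benefit over quarterly testing.

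A reader might also infer that the 30 days was taken from the monthly simulation. The figures coincide, but 8.2 reports no days and makes no link, so the origin is unknown.

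Nor is the criterion uninformative. If success meant a sample mean of at least 30 days among about 30 crossers (SD about 25–26 days), perfect weekly testing would reach it in about 93–99% of trials and monthly testing in about 21–56%. Section 8.3 does not state that rule, however; it names a rank sum test.

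The adherence point is limited too. Removal under 3.3.1 is discretionary, and adherence to weekly testing is a secondary hypothesis, so poor adherence would be examined directly.

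Finally, 8.2 says the sample size was set by recruitment capacity, so the simulation did not determine n, and the re-run ignores the MIP trigger. Both are true. Neither makes the stated 47.0% and 0.964 apply to weekly testing.

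**Conclusion.** The concern holds in limited form. The figures in 8.2 describe monthly sampling and are wrong for a trial that tests weekly: FVC at recommendation should be about 49%, not 47.0%, and the effect size about 1.7, not 0.964. The expected lead over quarterly testing is about 41 days with weekly sampling (range 37–42) and about 30 days with monthly sampling (27–31). The 30-day criterion is a legitimate floor against the three-month standard, but meeting it says nothing on whether weekly testing adds to monthly.

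This is not a finding that the trial is underpowered. The mismatch understates the simulated effect, and because both randomised arms test weekly, the simulated comparison is not one between the arms.

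The sizes rest on an assumed start FVC, accurate tests, an FVC-only trigger and full adherence. The mismatch between the simulated and actual schedules rests on the text alone.

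**What to change.** 1. In 8.2, re-run the simulation with weekly sampling. Report the outcome in days as well as FVC, state the start FVC used, and restate the figures (about 49%, about 41 days and an effect size of about 1.7 under the assumptions above).
2. In 1.1 and 8.3, keep 30 days as the floor against three-monthly testing. Give its justification, and state in 8.3 that reaching it supports a benefit over quarterly testing only.
3. In 8.3, add a secondary paired estimate: thin each participant's weekly series to every fourth test and report the within-participant difference in first threshold crossing, with its 95% CI (expected about 11 days, ±3 to 4 with about 30 crossers). Base any statement that weekly adds to monthly on this estimate.

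Two details should be fixed in advance for item 3. The difference cannot be negative, because the thinned tests are a subset of the weekly ones, so it should be read for its size and not tested against zero. Home testing also stops when NIV starts (7.2.2), so some four-weekly crossings will not be observed; the plan should say how these are dated, for example at the next four-weekly test date, and which of the four possible starting weeks is used.

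The cost is one simulation re-run, one extra secondary analysis and a few sentences. No new patients, visits or data are needed.

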1.2 Primary Study Endpoints

Part 1: The primary endpoint is completion of a standard PFT and an experimental rPFT during a single clinic appointment. At the endpoint, study outcomes will include:

- 1) The best forced vital capacity (FVC) and maximal inspiratory pressure (MIP) results from that visit's PFT
- 2) The best FVC and MIP results from that visit's rPFT
- 3) Survey responses from study participants.

Part 2: The primary endpoint for Aim 1 occurs at the clinic visit following initiation of NIV. At this time, participants will have had weekly measurements of FVC and MIP from self-administered rPFT procedures, as well as standard PFT assessments performed with the assistance of the respiratory therapist at approximately three-month intervals during standard in-person or telehealth clinic appointments. The primary endpoint for Aim 2 will be the change in self-efficacy scores from baseline. Changes will be compared across arms.

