3.2 Exclusion Criteria

Part 1

Patients:

- 1) Cognitive impairment, as judged by the ALS clinic neurologist, that prevents participation in the study.
- 2) Unable to perform pulmonary function testing with mouthpiece or with mask, as determined by one of the study investigators.

Caregivers: None

Controls: None

Respiratory Therapists: None

Part 2 imposes additional exclusion criteria for patients only.

Patients:

- 3) Use of NIV or diaphragm pacer at time of obtaining informed consent.
- 4) FVC \leq 50% predicted

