7.0 Study Design and Procedures

7.1 Study Design

Part 1: This is a self-controlled study where each participant will be administered a standard of care PFT for measurement of FVC and MIP, as well as an rPFT, separated by at least an hour, for measurement of

experimental FVC and MIP. The rPFT is guided by a respiratory therapist in another room, utilizing the telemedicine interface of the Hersey ALS clinic and devices for measuring FVC and MIP (**Error! Reference source not found.**).

[figure not shown]

Figure 3: Tools for remote pulmonary testing. Left: Air Smart Spirometer and turbine. Right: respiratory pressure meter and mouthpiece.

Part 2: This is a two-arm, randomized study to determine 1) whether weekly monitoring of respiratory function can lead to timelier initiation of NIV and 2) whether structured nurse coaching leads to improved self-efficacy for managing disease and better maintenance of respiratory health. For enrollees in both arms, standard FVC and MIP measurements obtained approximately every three months by the respiratory therapist during ALS Clinic are supplemented with self-administered rPFTs performed weekly. To train the participant in the performance of rPFTs, a member of the research team will be present either in person or virtually to guide the patient and caregiver in the appropriate use of the equipment during the first four weeks of the study. Enrollees in the NRHC arm will additionally receive monthly coaching with the study nurse via telehealth. Approximately 5% of NRHC sessions will include audio recordings that will be evaluated by a second clinician nurse for quality and consistency.

rPFT protocol

Two devices are used to measure respiratory function:

- 1) Air Smart Spirometer, NuvoAir AB

The following information is paraphrased from the user manual, which is included in the “devices” page of the protocol.

The Air Smart Spirometer measures the forced vital capacity (FVC) in a forced expiratory maneuver. The Air Smart Spirometer is intended to be used by:

- Healthcare professionals trained to perform spirometry tests on patients.
- Adults trained by healthcare professionals or through self-learning who understand how to perform a high quality spirometry test.

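### Aim 1's outcome is one time difference per participant, but section 8.3 assigns an unpaired two-sample test with no 30-day null, and no power is given for that difference

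*Combined protocol and SAP*

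**What the plan says.** Section 1.1 gives the Aim 1 hypothesis as "thresholds for non-invasive ventilation (NIV) recommendation to be met on average 30 days sooner when measured weekly", compared with the usual three-month interval. It describes the arms of Part 2 as follows: "both perform weekly rPFT testing and one receives monthly NRHC". Section 7.1 adds: "For enrollees in both arms, standard FVC and MIP measurements obtained approximately every three months by the respiratory therapist", with the weekly home tests on top. Every participant therefore contributes both kinds of measurement.

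The Figure 4 legend in section 7.2.2 names the primary outcome of Aim 1: the interval, Delta, between the moment NIV need is first detected and the scheduled clinic visit that follows. It shows an example of 60 days. Section 1.2 gives the timing: "The primary endpoint for Aim 1 occurs at the clinic visit following initiation of NIV".

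Section 8.3 says the analysis will determine whether the "study date of NIV initiation is at least 30 days sooner based on rPFTs compared to standard clinic PFTs", and then: "This will be done using a non-parametric two sample test of means, the Wilcoxon-Mann-Whitney rank sum test". For Aim 1 it states no samples, null value, alpha, sidedness or confidence interval; the sentence on confidence intervals follows the Aim 2 model.

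Section 8.2 says the sample size was fixed by expected recruitment. It then gives 80% power for 15 per arm at an effect size of 0.95. In support it reports a simulation of 40 people, half assessed monthly and half quarterly, with FVC at recommendation as the outcome.

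**The concern.** The outcome is a single within-person difference, and the named test compares two independent samples. Section 8.3 leaves two candidates for those samples. If they are the rPFT-based and clinic-based dates, both come from the same people and the pairing is lost. If they are the randomized arms, the contrast is coaching against no coaching, because both arms test weekly. Neither answers whether weekly testing gains 30 days.

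The target appears in the question but not in the test. A rank-sum test with a null of no difference cannot establish 30 days. It is also not a test of means, whereas section 1.1 speaks of an average.

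The event differs too. Sections 1.1 and 7.2.2 concern a threshold being met or a need being identified; section 8.3 concerns NIV initiation. A participant has at most one actual initiation date, so an rPFT-based initiation date and a clinic-based one cannot both be observed.

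Finally, a reader of section 8.2 has no power figure for Delta in days.

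**Working it through.** **1. The plan's 80%.** Forty completers in two arms is 20 per arm, and 0.75 × 20 = 15. For two independent groups the noncentrality is 0.95 × √(15/2) = 2.60 on 28 degrees of freedom. Against a one-sided 5% critical value of 1.70, power is 81%; against the two-sided value of 2.05 it is 71%. The stated 80% reproduces only as a one-sided figure, and 8.2 states neither alpha nor sidedness.

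**2. What the effect size measures.** The simulation was re-run with independent monthly declines of 3.5 ± 3.4 and an assumed starting FVC of 75 ± 15, truncated above 50. About 81% met the criterion, FVC at recommendation was 47.0 (monthly) and 43.3 (quarterly), and the effect size was 0.97. Section 8.2 reports 80.6%, 47.0, 43.4 and 0.964. The effect size of 0.95 therefore matches an FVC difference between people tested monthly and other people tested quarterly. Part 2 has no quarterly-only group, tests weekly, and measures Aim 1 in days.

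**3. A simple model of Delta.** The documents give no mean or SD for Delta. Assume visits every 13 weeks (91 days), a crossing equally likely in any week, and weekly detection without error. Delta then takes the values 0, 7, …, 84 days.

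- Mean = 42 days; SD = 7 × √((13² − 1)/12) = 26.2 days.
- With 30 crossers (75% of 40), the standard error of mean Delta is 26.2/√30 = 4.8 days and the 95% half-width is 2.05 × 4.8 = 9.8 days.
- The lower limit exceeds 30 only if the observed mean exceeds 39.8 days. The noncentrality is (42 − 30)/4.8 = 2.5, so power is about 68% two-sided and 79% one-sided at 0.05.

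**4. Why the rank-sum test fails on the same data.** Let crossings be spread over 364 days. Dates then vary between people with SD 364/√12 = 105 days. Treated as independent samples of 30, a difference in dates has standard error 105 × √(2/30) = 27 days, against a true paired value of 4.8.

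- After a 30-day shift the remaining 12 days is 12/27 = 0.44 standard errors, so the test almost never rejects.
- With no shift, 42/27 = 1.55, just short of the critical value, so the result depends on how spread out the dates are. In simulation at n = 30 and one-sided 0.05, the unshifted test rejects in 59% and the shifted test in 0%.
- A paired signed-rank test against zero rejects in 100%, including when the true mean gain is 28 days. Delta cannot be negative by definition, so a zero null says nothing about 30 days.

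**5. Ten illustrative scenarios.** Decline follows 8.2 (3.5 ± 3.4 per month), as persistent slopes or independent monthly steps. Starting FVC is assumed uniform over 65-82, 60-90, 55-85, 51-80 or 51-100%. Only the FVC threshold is modelled, with 13-week visits, 30 crossers, full weekly adherence and two-sided 0.05 unless stated.

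- Mean Delta 40-44 days; SD 25-27; correlation of the two dates 0.94-0.97.
- Unshifted rank-sum significant: 6-90%, depending on the spread of starting FVC.
- Rank-sum with 30-day shift significant: 0-1.0%.
- Lower 95% limit of mean Delta above 30: 53-82% (67-89% at one-sided 0.05).
- Signed-rank test of Delta minus 30: 47-79%.

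With visit intervals of 11-15 weeks the lower-limit rule gives 60-84% and the shifted rank-sum 0-0.4%. At 75% weekly adherence the lower-limit rule gives 36-68%.

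**6. Two features of Delta itself.** Section 7.2.2 omits the rPFT in clinic weeks, so some crossings are first seen at a visit: 6-9% of crossers at full adherence. Setting these to zero instead of excluding them lowers mean Delta by 3-4 days. Also, Delta starts at the first low reading whether or not the next visit agrees. With an assumed 4-point reading error, about 80% of first crossings occur while true FVC is above 50%, and 25-32% of next visits read above 50%.

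**The case against.** Section 8.3 does not say which samples are ranked, and its test sentence refers back to the question of at least 30 days, so a shifted test is a possible reading. That is fair, but it does not rescue the plan: the shifted version is the one that almost never confirms a gain of about 40 days. Nor is the unpaired choice a house style, since 8.3 uses a paired test for the within-person comparison in Part 1.

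Four stronger readings are tempting and should not be drawn.

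- A reader might infer that sections 1.1, 1.2, 7.2.2 and 8.3 give four rival definitions of the event. They do not. Section 1.2 states when the endpoint occurs, and 1.1 and 7.2.2 are close in meaning. The real split is need identified against NIV initiated.
- A reader might infer that 8.2 claims 80% power for Aim 1, or that N is wrong because of it. Section 8.2 speaks only of a mean outcome, never names Aim 1, and says recruitment set the number.
- A reader might infer that the unshifted test would often support a false 30-day claim when the true gain is much smaller. That depends on everyone sharing fixed 13-week visits; section 7.1 says only that visits are approximately three-monthly, and the effect shrinks sharply once visit times vary.
- A reader might take the simulated percentages as the trial's power. MIP, the other trigger, is not modelled, and starting FVC is assumed.

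One further objection stands against the remedy: measurement error in a single home reading counts as gain, so analysing Delta alone can flatter weekly testing. The fix has to address this.

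**Conclusion.** The point holds and should be corrected before analysis. The mismatch between a within-person outcome and an independent-samples test follows from the text alone, as do the missing 30-day null and the comparison of initiation dates that cannot both be observed. None of these depends on the simulation.

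The size is illustrative. Under the step 5 assumptions at full adherence, a real mean gain of 40-44 days is confirmed in about 0-1% of trials by a shifted rank-sum test and in 53-82% by the lower limit of mean Delta. The unshifted result swings from 6 to 90% while mean Delta barely moves. The 80% in 8.2 is not an arithmetic error if one-sided, but its supporting simulation is a two-group FVC contrast absent from Part 2, and no power was calculated for Delta.

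**What to change.** In section 8.3, replace the rank-sum test for Aim 1 with a one-sample (paired) analysis of Delta, pooled over arms. Report mean Delta with a 95% CI judged against 30 days, with a signed-rank test of Delta minus 30 as a check. State alpha and sidedness, and do not test against zero.

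Use one event, threshold first met or need identified, in sections 1.1, 7.2.2 and 8.3, and align the endpoint timing in 1.2.

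Pre-specify how crossings first seen at a clinic visit enter; Delta = 0 is one option, with a sensitivity analysis. Report the numbers of non-crossers and of crossers with no later visit. Report the share of next clinic visits whose own PFT also meets the threshold, and repeat the analysis in crossings confirmed in that way. This is an analysis definition only and changes no clinical rule.

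In section 8.2, say that the 80% refers to a two-group FVC contrast, and restate power for mean Delta against 30 days with its assumptions, including adherence.

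The cost is wording in five sections, with no new data or participants. The downside is that the 30-day claim becomes harder to meet. Restated power may fall below 80%, and with a half-width of about 10 days, a gain that is estimated without establishing 30 days is a realistic result.
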